### Day -1 Each Cycle:

1. Check Cockcroft-Gault estimate of Creatinine clearance. If < 100mL/min, order 24-hour creatinine clearance.
2. Confirm at least 7 days serum methotrexate  $\leq$  0.05 mcmol/L from previous cycle to next dose of methotrexate.
3. Evaluate for possible methotrexate dose adjustments based on toxicities from previous cycle.

### Day 1 of each cycle:

1. Review all concomitant medications prior to day 1 of each cycle. Discontinue any drug that would have interaction with methotrexate excretion. See list below. No filgrastim within 24 hours before methotrexate administration.
2. Rituximab 375 mg/m^2
3. Start IV fluid hydration by 18:00, using one of the protocol specified alkalinized IVF order sets in CRIS for 06-C-0051
4. Order q6 hour urine pH  $\geq$  7.0 (00:00, 6:00, 12:00, 18:00) and **STRICT URINE OUTPUT** monitoring record urine output every hour
5. Draw the following blood work until methotrexate level is < or equal to 0.05 mcmol/L:
  - a. Hepatic panel every other day
  - b. CBC/Diff, Chem 7 daily

**Day 2:**

1. 7 am: notify MD of urine pH and hourly UOP. If UOP < 100mL/hour or urine pH <7 or >8, adjust IVF.
2. Methotrexate 6000 mg/m^2. Order within the 06-C-0051 CRIS order set. Include Sodium Bicarbonate 45mEq as an additive. (May be adjusted between 25-75mEq depending on individual patient needs).
  - a. For creatinine clearance 60-100 mL, adjust methotrexate dose using formula: (Creatinine Clearance)/100 x 6000 mg/m^2
  - b. For creatinine clearance < 60ml/min, methotrexate **will NOT be administered**.
  - c. If episodic AST/ALT elevation > 10X upper limit normal on previous cycle, decrease methotrexate by 25%
3. Goal Start time: administer methotrexate starting between 9:00-10:00 am

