##### 3.1.1.2 Laboratory abnormalities that make the protocol therapy unsafe to administer:

###### 3.1.1.2.1 Platelet count <50,000/mm^3

- 3.1.1.2.2 Inability to obtain an absolute neutrophil count  $>1000$  cells/mm^3 despite use of filgrastim for at least 5 days (see section 3.3.5.6)
- 3.1.1.2.3 ALT and/or AST  $>2$  X upper limit of normal unless due to antiretroviral therapy or other necessary medications, in which case ALT and AST exclusion cut-off is  $>5$ X upper limit of normal
- 3.1.1.2.4 Bilirubin  $>2$  X upper limit of normal unless due to protease inhibitor therapy
- 3.1.1.2.5 Creatinine  $>1.5$  mg/dL, unless estimated or measured creatinine clearance is  $\geq 60$  mL/min.
  - If creatinine clearance estimated with the method of Cockcroft and Gault is  $<100$  mL/min, a measured creatinine clearance should be obtained.
- 3.1.1.3 Patients with Class III or higher New York Heart Association Classification of Congestive Heart Failure unresponsive to treatment that would make hydration infeasible.
- 3.1.1.4 Evidence of other opportunistic diseases or complications of HIV infection that would make the protocol therapy infeasible to administer. Examples include, but are not limited to:
  - 3.1.1.4.1 Aggressive symptomatic Kaposi's sarcoma requiring systemic therapy
  - 3.1.1.4.2 Uncontrolled systemic and/or CNS-invasive fungal infection
- 3.1.1.5 Hypersensitivity to murine proteins or any component of rituximab
  - Patients who are ineligible to receive rituximab, high-dose methotrexate and leucovorin will be treated with "Radiation-sparing Best Available Care", as outlined in Section 3.6.

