**Figure 1: Study Schema: Eligibility Evaluation and Initial Therapy**

### **3.2 PHASE II STUDY DESIGN FOR HIGH-DOSE METHOTREXATE WITH LEUCOVORIN RESCUE AND RITUXIMAB**

Induction treatment cycles with rituximab, high-dose methotrexate and leucovorin will be administered every 2 weeks for 6 cycles. Two additional consolidation cycles of high-dose methotrexate without rituximab will be administered at 4 weeks and 8 weeks following completion of the combined therapy.

MRI will be repeated at the end of cycles 2, 4, 6, and 8, and additionally as clinically indicated. At the time of first evidence for complete tumor response by MRI criteria, FDG-PET scan and EBV DNA assessments of the blood and CSF will be repeated. If there is not a complete response by end of cycle 6, patients will be categorized as treatment failures and will not receive the two additional high-dose methotrexate doses. At end of treatment, restaging by MRI will be performed once every 2 months x 3; then once every 3 months x 6; then once every 6 months x 2; then as clinically indicated or annually up to year 5. After this period, clinical evaluations may continue and restaging

performed if clinical suspicion of CNS pathology. Additionally, FDG-PET scan will be repeated as outlined in section 3.8.4.2. (See also Appendix 3).

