3.4.2 High-dose methotrexate

3.4.2.1 The creatinine clearance (CrCl) will be calculated by method of Cockcroft-Gault prior to each cycle (see [Appendix 4](#)). If CrCl is  $\geq 100$  mL/min, then no dose adjustment is necessary. If CrCl is  $< 100$  mL/min, then the methotrexate dose is adjusted by the fraction of CrCl less than 100 mL/min (e.g., methotrexate dose =  $6000 \text{ mg/m}^2 \times \text{CrCl}/100$ ).

3.4.2.1.1 For estimated creatinine clearance  $< 100$  mL/min, a 24-hour urine collection should be obtained *plus* a serum creatinine at the end of the collection period to determine a measured creatinine clearance.

3.4.2.2 Delayed methotrexate serum clearance ( $> 3$  days after methotrexate infusion) may occur and mandates accelerated rescue and continued hydration and alkalinization. The minimum interval between achieving a serum methotrexate level  $\leq 0.05 \text{ mcg/mL}$  and the start of a subsequent treatment cycle is 7 days.

3.4.2.3 For creatinine clearance  $< 60$  mL/min, no methotrexate will be administered. Administer rituximab without methotrexate after discussion with a medically responsible investigator if renal function cannot be expected to be optimized (CrCl  $\geq 60$  mL/min) within 3 days.

3.4.2.4 For transient ALT and/or AST elevations  $\geq 10X$  the upper limit of normal, withhold methotrexate until both ALT and AST are  $\leq 5X$  the upper limit of normal, then permanently reduce methotrexate dosage by 25% for all subsequent cycles beginning with the next cycle.

3.4.2.5 For ANC  $< 1000 \text{ cells/mm}^3$ , delay methotrexate until ANC recovers to  $\geq 1000/\text{mm}^3$ .

3.4.2.6 For platelet counts  $< 50,000/\text{mm}^3$ , delay methotrexate until platelet count recovers to  $\geq 50,000/\text{mm}^3$ .

3.4.2.7 For any other Grade 3 or greater toxicities related to methotrexate, with the exception of hematologic toxicity, hold methotrexate until toxicity abates to Grade  $\leq 2$ .

3.4.2.8 For pulmonary toxicity related to methotrexate, permanently discontinue methotrexate.

3.4.2.9 Note, if toxicity attributed to methotrexate prevents subsequent methotrexate treatment prior to the time of complete response, patient will be considered a treatment failure. Failure of toxicity to resolve and thus creating dose delays in excess of 15 days will result in methotrexate discontinuation.

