**Day 3-End Leucovorin Rescue:**

1. Start leucovorin 100 mg/m^2 IV q6 hours starting 24 hours **AFTER INITIATION** of methotrexate administration.
2. Serum methotrexate monitoring levels is now performed at Children's Hospital 7 days a week at 2 p.m. Specimens collected for methotrexate monitoring must be delivered to the NIH CC Department of Laboratory Medicine's Chemistry Service in the morning so they can be delivered to Washington's Children's Hospital and processed in a timely manner. This process is designed to obtain same day results for patients on 06-C-0051 so the clinical team can make protocol defined treatment decisions, such as stopping leucovorin or IV fluids, or implementing treatment of delayed methotrexate clearance with glucarpidase (Voraxaze®).
3. 24 hours **AFTER INITIATION** of methotrexate, draw red top tube for serum methotrexate level. Methotrexate Levels need to be **drawn at scheduled time**.
4. Repeat every 24 hours: 48 hr, 72 hr, 96 hr, until methotrexate monitoring no longer required.
5. Check methotrexate levels same day, evaluate for delayed methotrexate clearance. Notify Research team for:
  - a. Methotrexate > 10 mcg/L at 24 hours
  - b. Methotrexate > 1 mcg/L at 48 hours
  - c. Methotrexate > 0.1 mcg /L at 72/hours
  - d. For **delayed methotrexate** elimination see pages 26 and 27 3.4.3), Table 1 (Leucovorin dose at 24, 48, 60 and 72 hours), and 3.4.4 for use of glucarpidase guidelines.
6. Stop **intravenous** leucovorin and switch to oral leucovorin 25 mg PO (Alternative 10 mg/m^2 PO) q6 hours
  - a. If methotrexate level is <0.5 mcg/L, see section 3.3.4.3.2
  - b. Patient does **NOT** have delayed methotrexate clearance (Defined, Point 5 above.)
  - c. Discuss discontinuing IVF research team

7. Stop **oral** leucovorin and urine monitoring once serum methotrexate level is  $\leq$  0.05 mcmol/L

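### Appendix 9 limits the 25% methotrexate cut for liver toxicity to the cycle after the event; Section 3.4.2.4 makes it permanent

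*Combined protocol and SAP*

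**What the plan says.** Two current parts of the protocol give a methotrexate rule for transaminase elevations.

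- **Section 3.4.2.4.** The trigger is ALT and/or AST at or above 10 times ULN. Methotrexate is withheld until both are at or below 5 times ULN, and the instruction is "then permanently reduce methotrexate dosage by 25% for all subsequent cycles beginning with the next cycle".
- **Appendix 9, Day 2, item 2.** Every cycle's order starts from 6,000 mg/m², with the direction "Order within the 06-C-0051 CRIS order set". Item 2c then says: "If episodic AST/ALT elevation > 10X upper limit normal on previous cycle, decrease methotrexate by 25" per cent. It mentions neither permanence nor the hold.
- **Appendix 9, Day -1, item 3.** The pre-cycle toxicity review uses the same look-back: "Evaluate for possible methotrexate dose adjustments based on toxicities from previous cycle".

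Some Appendix 9 items send the reader to the body. In the Day 3 block, item 5d points to 3.4.3 and 3.4.4, and item 6a says "see section 3.3.4.3.2". Item 2c cites nothing. No text says whether the body or the appendix governs if they differ.

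**The concern.** Appendix 9 is the working guide for giving a high-risk drug cycle by cycle. If its rule looks back one cycle only, a patient whose dose was cut for liver toxicity, and who then has a clean cycle at the reduced dose, no longer meets the condition for the cut. The checklist would put that patient back on full dose, which 3.4.2.4 rules out.

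Such an event is plausible here. Section 3.1.1.2.3 excludes ALT or AST above 2 times "upper limit of normal unless due to antiretroviral therapy or other necessary medications, in which case ALT and AST exclusion cut-off is" above 5 times. A patient entering at 5 times ULN on antiretrovirals needs only a doubling to reach the 3.4.2.4 trigger. Section 9.2.7.6 links hepatitis on high-dose methotrexate to prolonged, high serum levels, while calling it uncommon. A team that followed the checklist would also create a protocol deviation, and 8.2.1 requires all deviations to be reported.

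**Working it through.** **Which reading of the look-back is natural.** Day -1 item 2 of Appendix 9 requires at least 7 days at or below 0.05 mcmol/L between the previous cycle and the next methotrexate dose. There, the previous cycle can only be the one just completed. Items 2c and Day -1 item 3 use the same phrase, so the one-cycle reading is the natural one.

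**Inputs.** Full dose 6,000 mg/m² (3.3.4.2). Reduced dose 6,000 × 0.75 = 4,500 mg/m². Cycles given: n = 8 (six induction, two consolidation, Section 3.2), or n = 6 for patients without a complete response by the end of cycle 6, who "will not receive the two additional high-dose methotrexate doses".

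**Assumptions.** One qualifying event (above 10 times ULN) in cycle k, recovery in time to continue, no repeat, all n cycles given, and creatinine clearance at least 100 mL/min. With clearance of 60 to 100 mL/min, the literal checklist returns to the renally scaled dose without the 25% cut.

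**Per cycle.**

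| Cycle | Section 3.4.2.4 | Appendix 9, literal |
|---|---|---|
| k+1 | 4,500 | 4,500 |
| k+2 onward | 4,500 | 6,000 |

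Ratio from k+2: 6,000 / 4,500 = 1.33, or +33%.

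**Cumulative, in g/m², for k < n.**

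- Section 3.4.2.4: 6k + 4.5(n − k)
- Appendix 9, literal: 6k + 4.5 + 6(n − k − 1) = 6n − 1.5
- Excess: 1.5(n − k − 1)

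| k | n = 8: 3.4.2.4 | n = 8: App. 9 | Excess | n = 6: 3.4.2.4 | n = 6: App. 9 | Excess |
|---|---|---|---|---|---|---|
| 1 | 37.5 | 46.5 | +24.0% | 28.5 | 34.5 | +21.1% |
| 2 | 39.0 | 46.5 | +19.2% | 30.0 | 34.5 | +15.0% |
| 3 | 40.5 | 46.5 | +14.8% | 31.5 | 34.5 | +9.5% |
| 4 | 42.0 | 46.5 | +10.7% | 33.0 | 34.5 | +4.5% |
| 5 | 43.5 | 46.5 | +6.9% | 34.5 | 34.5 | 0 |
| 6 | 45.0 | 46.5 | +3.3% | – | – | – |
| 7 | 46.5 | 46.5 | 0 | – | – | – |

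An event in the last cycle given has no later dose to change.

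**Threshold.** The triggers (at or above 10 times, and above 10 times) differ only at exactly 10 times ULN. There the body cuts the dose and the checklist does not.

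**How many patients.** The documents give no event rate. Assuming a rate p among the 15 main-cohort patients, the expected number is 15p and the chance of at least one event is 1 − (1 − p)^15:

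| Assumed p | Expected patients | Chance of at least one |
|---|---|---|
| 0.02 | 0.3 | 26% |
| 0.05 | 0.75 | 54% |
| 0.10 | 1.5 | 79% |

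These are chances of a qualifying event. A dosing error also needs a cycle k+2 and a team that follows the checklist without 3.4.2.4.

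**The case against.** The best defence is that Appendix 9 never tells anyone to restore the dose. It is silent on cycle k+2, and 3.4.2.4 fills that silence explicitly. The appendix is also plainly not a complete dosing source. Its Day -1 and Day 2 steps omit the rules on neutrophils, platelets, other Grade 3 toxicity, pulmonary toxicity and the 15-day delay limit (3.4.2.5 to 3.4.2.9). Its Day -1 toxicity review gives no criteria, so a clinician has to open 3.4.2 and would see the permanent reduction there. The order set might carry the right rule. Some affected patients would stop methotrexate under the 15-day limit and never reach cycle k+2. A doubling reaches the trigger only from the 5-times entry limit; from the ordinary 2-times limit a fivefold rise is needed.

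Much of this stands as a limit on how often harm would follow. It does not remove the conflict. The checklist is not silent on the starting dose: each cycle begins at 6,000 mg/m², and the cut applies only if its condition is met. Items 2a and 2b reproduce the renal rules of 3.4.2.1 and 3.4.2.3 correctly, so a user has reason to trust 2c as well. Reliance on staff remembering the body text is weak over the 6 to 10 years of accrual expected in 6.1.3.

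**Conclusion.** The inconsistency is real and lies between two current texts. Read literally, Appendix 9 reverses, from the second cycle after the event, a reduction that 3.4.2.4 makes permanent. On the stated assumptions this is 33% more methotrexate per affected cycle, and up to 24.0% more over eight cycles or 21.1% over six. The permanence conflict is what matters. The threshold difference is trivial, and the missing hold is an omission, not a contradiction.

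Few patients are likely to be affected, and nothing in the documents shows that anyone would be misdosed, because the order set cannot be seen. The primary endpoint, the sample size of 15 and the power are untouched. It should still be corrected: a dosing checklist that undoes a safety reduction when followed as written contains a wrong rule.

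**What to change.** State that 3.4.2.4 governs, and align Appendix 9 with it:

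- **Day 2, item 2c:** if ALT and/or AST was ≥10X ULN in any previous cycle, give no methotrexate until both are ≤5X ULN, then reduce by 25% for every later cycle (see 3.4.2.4).
- **Day -1, item 3:** extend the toxicity review to any previous cycle.
- **Order set:** confirm that it carries the reduction forward.

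Section 3.4.2.4 itself does not say whether a second event brings a further 25% cut, or how the cut combines with renal scaling. Both could be settled in the same amendment, but the correction does not depend on them.

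The cost is two lines of text and one check of the order set. Hepatic panels are already drawn on Day 1 of each cycle (3.8.3), so no visit or test is added, and sample size and power stay as they are.

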**Day 3-End Leucovorin Rescue:**

1. Start leucovorin 100 mg/m^2 IV q6 hours starting 24 hours **AFTER INITIATION** of methotrexate administration.
2. Serum methotrexate monitoring levels is now performed at Children's Hospital 7 days a week at 2 p.m. Specimens collected for methotrexate monitoring must be delivered to the NIH CC Department of Laboratory Medicine's Chemistry Service in the morning so they can be delivered to Washington's Children's Hospital and processed in a timely manner. This process is designed to obtain same day results for patients on 06-C-0051 so the clinical team can make protocol defined treatment decisions, such as stopping leucovorin or IV fluids, or implementing treatment of delayed methotrexate clearance with glucarpidase (Voraxaze®).
3. 24 hours **AFTER INITIATION** of methotrexate, draw red top tube for serum methotrexate level. Methotrexate Levels need to be **drawn at scheduled time**.
4. Repeat every 24 hours: 48 hr, 72 hr, 96 hr, until methotrexate monitoring no longer required.
5. Check methotrexate levels same day, evaluate for delayed methotrexate clearance. Notify Research team for:
  - a. Methotrexate > 10 mcg/L at 24 hours
  - b. Methotrexate > 1 mcg/L at 48 hours
  - c. Methotrexate > 0.1 mcg /L at 72/hours
  - d. For **delayed methotrexate** elimination see pages 26 and 27 3.4.3), Table 1 (Leucovorin dose at 24, 48, 60 and 72 hours), and 3.4.4 for use of glucarpidase guidelines.
6. Stop **intravenous** leucovorin and switch to oral leucovorin 25 mg PO (Alternative 10 mg/m^2 PO) q6 hours
  - a. If methotrexate level is <0.5 mcg/L, see section 3.3.4.3.2
  - b. Patient does **NOT** have delayed methotrexate clearance (Defined, Point 5 above.)
  - c. Discuss discontinuing IVF research team

7. Stop **oral** leucovorin and urine monitoring once serum methotrexate level is  $\leq$  0.05 mcmol/L

**Medications to avoid during Methotrexate administration:**

1. Asparaginase
2. Aspirin
3. Acidic drugs
4. Amoxicillin
5. Cephalosporins
6. Chloramphenicol
7. Cholestyramine
8. Cotrimoxazole
9. Cyclosporine
10. Diclofenac
11. Ibuprofen
12. Indomethacin
13. Ketoprofen
14. Mercaptopurine
15. Mezlocillin
16. Naproxen
17. Non-steroidal anti-inflammatory drugs
18. Omeprazole
19. Penicillins
20. Piperacillin ( $\pm$ tazobactam)
21. Probenecid
22. Proton pump inhibitors (e.g., dexlansoprazole, esomeprazole, lansoprazole, omeprazole, pantoprazole, rabeprazole)
23. Pyrimethamine
24. Salicylates
25. Sulfonamides
26. Sulindac
27. Tetracyclines
28. Tolmetin
29. Trimethoprim
30. Trimethoprim/sulfamethoxazole
31. Vaccines, Live (viral and bacterial)
